3.1. Overall Study Design and Plan

This is a Phase 2A, randomized, double-blind, placebo-controlled, single dose, sequential group study. Part A evaluates the safety, tolerability, PK and PD of PB2452 vs matching placebo with ticagrelor + ASA pretreatment when various dose levels and administration regimens are administered to 1) healthy older (age 50 to 64 years) and elderly (age 65 to 80 years) male and female subjects in Part A. Part B investigates various dose levels and regimens of PB2452 administered to healthy male and female subjects (ages 18-50) pretreated with a high dose of ticagrelor alone (180 mg) twice daily (BID).. All references to study drug within this SAP apply to PB2452 or matching placebo. Part B evaluates the safety, tolerability, PK and PD of PB2452 vs matching placebo with High Dose of ticagrelor + ASA pretreatment to healthy male and female subjects. All references to study drug within this SAP apply to PB2452 or matching placebo.

Each cohort was planned to include approximately 8 to 12 subjects randomized in a 3:1 ratio, PB2452:placebo.

PART A:

The initial cohort (Cohort 1) included approximately 8 subjects ages 50 to 80 years pretreated with ASA + ticagrelor randomized to 18 grams (g) of PB2452 or matching placebo administered as an initial 6 g bolus infused over 10 minutes, followed by 12 g infused over the next 15 hours and 50 minutes to complete a 16 hour administration regimen.

Following completion of Cohort 1, a subsequent cohort was tested, also at an 18 g dose level of PB2452 or matching placebo in the same population as in Cohort 1. A written Dosing Memo was provided by the Sponsor to the clinical site describing details of the dosing regimen, cohort population, cohort size, sampling schedules, and other cohort-specific study activities prior to initiation of each cohort. The maximum total dose of PB2452 administered to any subject as not to exceed 30g. Duration of study drug infusions was not to exceed 48 hours. The maximum administration rate of PB2452 was not to exceed 18g over 30 minutes.

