11.1. Pharmacodynamic Data

Blood samples for PD analysis will be collected from subjects at the following time points: Day -3, before dosing (within 60 minutes prior to 1st ticagrelor dose on Day -2) and again before dosing (within 10 minutes prior to the initiation of the study drug infusion [Hour 0]), and up to 48 hours after the initiation of study drug infusion. Collection time points for each cohort will be specified in a Dosing Memo from Sponsor to PPD prior to initiation of each cohort. The

sampling schedule for a given cohort may differ from that of other cohorts to accommodate various infusion durations that may be examined in the protocol in order to fully characterize the PK/PD profile.

Specific collection times were identical for all 3 cohorts: Day -3, Day -2 (up to 60 minutes prior to 1st ticagrelor dose) and Hour 0 (up to 10 minutes prior to PB2452 infusion), 5 minutes, 0.25, 0.5, 1, 2, 4, 8, 12, 20, 24, 36 and 48 hours after initiation of PB2452 or placebo infusion

Platelet aggregation will be assessed using the VerifyNow, LTA and VASP assays. The results for the VerifyNow assay will be expressed as PRU and %baseline PRU, which will be calculated from the platelet aggregation-time profile for each sampling time point. The results of platelet aggregation from the LTA assay using 5 μ M ADP and 20 μ M ADP will be expressed as maximal-extent aggregation (MA), %baseline MA, final-extent aggregation (FA) and %baseline FA, which will be calculated from the platelet aggregation-time profile for each sampling time point. The results of platelet aggregation from the LTA assay using agonists 1.6 mM AA and 15 μ M TRAP will be included in SDTM PD dataset only and not included in tables, listings or figures. Similarly, PD results from the VASP assay will be expressed as PRI and %baseline PRI, which will be calculated from the platelet aggregation-time profile for each sampling time point.

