Blood drawn for LTA PD assessments will be further processed for testing soluble and surface P-selectin/CD62p after completion of LTA, as per instructions. All LTA timepoints will have samples processed for testing however only the time points as defined below are planned for testing P-selectin. The remaining samples will be stored, as per their stability profiles, for future testing if needed to help elucidate the results. The sampling schedule for P-selectin for subsequent cohorts will be specified in a Dosing Memo provided by Sponsor to PPD prior to initiation of each cohort.

Specific P-selectin collection times were: Day -2 (up to 60 minutes prior to first ticagrelor dose), Hour 0 (up to 10 minutes prior to PB2452 infusion), 12 and 24 hours.

Pharmacodynamic data will be listed by subject and ADA status and summarized for each treatment group for each time point using descriptive statistics (number of subjects, mean, SD, median, minimum, and maximum). Mean PD data versus scheduled time profiles will be presented graphically. Biomarker data (P-selectin) will be listed and summarized by each cohort for each time point using descriptive statistics (number of subjects, mean, SD, median, minimum, and maximum).

Scatter plots of PD data versus total and unbound PB2452 plasma concentrations will be prepared for all cohorts, as appropriate. A box plot of PD data versus sampling time point will be prepared for each dose level.

Scatter plots of CrCl versus total and unbound ticagrelor and TAM plasma concentrations will be prepared for all cohorts, as appropriate.

Correlation between VerifyNow assay, LTA assay, and VASP assay will be investigated graphically. Scatter plots of individual subject PRU versus MA (5 μ M ADP and 20 μ M ADP),

PRU versus PRI, and MA (5 μ M ADP and 20 μ M ADP) versus PRI will be plotted, and the correlation coefficient r (Spearman's rank correlation coefficient) and p-value will be displayed.

11.2. 10.2 Pharmacodynamic Parameters

Pharmacodynamic parameters will be calculated using actual timepoints using SAS[®] Version 9.4 or higher. Missing PD values will be treated as missing for PD parameter calculation.

The following PD parameters will be calculated using %baseline/actual PRU data from the VerifyNow assay.

Day 1 parameters following 5th ticagrelor dose	
APRUMax	Maximal actual PRU
APRUMax4h	Maximal actual PRU within 4 h
PRUmax	Maximal percent of baseline PRU
TPRUMax	Time to maximal actual PRU

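### SAP 11.1 prints a Spearman p-value for the PRU, MA and PRI pairs without naming the observations used or a method for repeated samples; with all 15 times per subject the p-value can be too small

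*SAP*

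**What the plan says.** SAP Section 11.1 introduces the comparison with "Correlation between VerifyNow assay, LTA assay, and VASP assay will be investigated graphically". It then asks for "Scatter plots of individual subject PRU versus MA" at 5 and 20 μM ADP, PRU against PRI, and MA at both ADP concentrations against PRI. That makes five pairings. On each plot, "the correlation coefficient r (Spearman's rank correlation coefficient) and p-value will be displayed".

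The same section defines the measurements by sampling time. VerifyNow results, for example, are "expressed as PRU and %baseline PRU, which will be calculated from the platelet aggregation-time profile for each sampling time point", with parallel wording for MA and PRI. It states "Specific collection times were identical for all 3 cohorts" and lists them. For the tables it does give a unit, since PD data are "summarized for each treatment group for each time point using descriptive statistics", but it does not carry that unit over to the correlations.

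Five things are not stated:
- which times enter r
- whether the two samples before ticagrelor count
- whether values are actual or percent of baseline
- whether cohorts, PB2452 and placebo are combined
- how repeated samples are handled

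SAP Section 4 says only that outputs are separate by Part. The missing-value rule in Section 11.2 concerns PD parameters. The pharmacodynamic analysis sections of both protocols (3.6.3.2) do not mention this correlation.

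**The concern.** A Spearman p-value needs a defined n and independent pairs. Here n could be the number of subjects, 15 per plot, or 15 times the number of subjects, and the plan does not choose.

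Two readings use every sampling time. In one, all pairs within a Part go on one plot. In the other, which the phrase about individual subjects also allows, each subject has a plot of 15 serial points. In both, the standard reference distribution assumes more information than the data hold.

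The same data could therefore carry very different p-values depending on an unstated programming choice, and a reader of the study report could take a very small one as strong evidence of assay agreement.

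**Working it through.** **Inputs from the documents**
- Sampling times (SAP 11.1): Day -3, Day -2 and Hour 0, then 12 times from 5 minutes to 48 hours. 2 + 1 + 12 = 15 per subject.
- Cohort size and allocation (SAP 3.1): "Each cohort was planned to include approximately 8 to 12 subjects randomized in a 3:1 ratio, PB2452:placebo".
- Part A: two cohorts enrolled (SAP 3.3). "The initial cohort (Cohort 1) included approximately 8 subjects ages 50 to 80 years". Cohort 2's size is not stated. At 8 to 12 it brings Part A to 16 to 20 subjects.
- Part B: one cohort of up to 12 (SAP 3.1 and 3.3).

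The plan gives no n, alpha or intraclass correlation (ICC) for these correlations, so it has no figure of its own to reproduce. A two-sided 0.05 level and the ICCs below are assumptions.

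**Step 1: pairs per plot.** Part B: 12 × 15 = 180. Part A: 16 × 15 = 240 to 20 × 15 = 300. One plot per subject: 15.

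**Step 2: smallest |r| with p < 0.05.** By the t approximation, |r| = t / √(t² + n − 2), with t the 97.5% quantile on n − 2 degrees of freedom.

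| Observations | n | t | smallest \|r\| |
|---|---|---|---|
| Part B, one value per subject | 12 | 2.228 | 0.576 |
| Part B, all pairs pooled | 180 | 1.973 | 0.146 |
| Part A, one value per subject | 16 to 20 | 2.145 to 2.101 | 0.497 to 0.444 |
| Part A, all pairs pooled | 240 to 300 | 1.970 to 1.968 | 0.127 to 0.113 |

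The unstated choice moves the threshold about fourfold.

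**Step 3: pooled pairs, unrelated assays.** With m = 15 times and ICCs a and b in the two assays, the variance of r is inflated by roughly D = 1 + (m − 1)ab. A nominal 5% test then rejects with probability 2[1 − Φ(1.96/√D)]. The simulated columns use two independent series, each a subject effect plus independent noise. The equal-ICC rows had 10,000 runs per setting.

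| ICC in the two assays | D | Formula | Simulated, 12 subjects | Simulated, 20 subjects |
|---|---|---|---|---|
| 0.1 and 0.1 | 1.14 | 6.6% | 6.3% | 6.0% |
| 0.2 and 0.2 | 1.56 | 11.7% | 10.4% | 11.0% |
| 0.4 and 0.4 | 3.24 | 27.6% | 26.0% | 25.8% |
| 0.6 and 0.6 | 6.04 | 42.5% | 41.0% | 41.4% |
| 0 and 0.6 | 1.00 | 5.0% | 5.0% | not shown |
| 0.1 and 0.6 | 1.84 | 14.8% | 13.7% | not shown |

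The rate hardly depends on the number of subjects. It depends on the product of the two ICCs, so clustering in one assay alone does no harm. With one value per subject the simulated rate is 5.2% (12 subjects) and 5.1% (20).

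**Step 4: one plot per subject, unrelated assays.** For 15 serial points with lag-1 correlation 0.3, 0.5, 0.7 and 0.9, the nominal 5% test rejects in 6%, 12%, 17% and 29% of 5,000 runs.

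**Step 5: assays that share a drug effect.** If both follow assumed active and placebo curves with a swing of 2 or 4 SD, pooled r is about 0.34 or 0.62. The SD of its Fisher z is 1.0 to 2.0 times the independent-sample value (ICC 0.2 to 0.6). Taking the worst ratio, SE = 2.0 × √(1.06/(n − 3)):
- r = 0.34, n = 180: 0.354/0.155 = 2.29, p ≈ 0.02.
- r = 0.34, n = 300: 0.354/0.120 = 2.96, p ≈ 0.003.
- r = 0.62, n = 180: 0.725/0.155 = 4.68, p < 0.00001.

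The corrected p-values are larger but stay below 0.05.

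**The case against.** The strongest reply is that unrelated assays are the wrong reference case. All three assays measure platelet reactivity under ticagrelor, and the Part A protocol (1.1.2) reports reversal in Phase 1 by multiple assays. A real association is likely, and Step 5 shows it would survive even a doubled standard error. The plots are described as graphical, no objective in SAP Section 2 concerns agreement between assays, and the Part B protocol (3.6.3.2) already treats efficacy results as descriptive because of the small sample. This part stands, and it is why the point is minor.

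The reply also limits three stronger inferences that a reader might draw:
- That the p-values will be wrong by a known amount, such as a 41% false-positive rate. The documents give no ICC, and inflation needs clustering in both assays. In some settings treating the samples as independent is adequate.
- That the SAP orders pooling. It does not. Pooling by Part is a natural reading, one plot per subject is another, and one value per subject would be close to nominal.
- That pooled r is itself invalid. It is a legitimate marginal association, provided it is described as including the time course common to both assays.

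The reply does not supply the missing unit of analysis. Nor does it give the p-value a valid reference distribution under either reading that uses all 15 times.

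**Conclusion.** The point holds as a minor one. The plan commits to a p-value without saying which observations produce it. Under either reading that uses all sampling times, the ordinary calculation treats serial samples as independent and can give too small a value.

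What is certain from the documents is the count: 15 samples per subject, hence up to 180 pooled pairs in Part B and about 240 to 300 in Part A, the latter assuming 8 to 12 subjects in Cohort 2. The size of the error is conditional. It is about 6% to 41% rejection at a nominal 5% for unrelated assays with equal ICCs of 0.1 to 0.6, about 5% if one assay is unclustered, and probably no change of conclusion if the drug effect on both assays is strong. No dose, safety or efficacy decision rests on the result.

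**What to change.** Amend SAP Section 11.1 to name the time points, treatment groups and scale that enter r, and remove the p-value. Suggested wording, if all times are to be used:

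*Plots will show actual values at all sampling times, separately for Part A and Part B, with points coded by treatment group and time. Spearman r is descriptive and reflects the ticagrelor and PB2452 time course common to the assays as well as any other association. No p-value will be shown.*

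If the sponsor prefers percent of baseline, or wants to leave out the samples before ticagrelor, the sentence should say so.

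If inference is wanted, either of these would serve, labelled approximate given the few subjects:
- One prespecified value per subject for each assay, with the ordinary Spearman test.
- A subject-level method on all times: leave-one-subject-out jackknife, resampling or permutation of whole subjects, or a repeated-measures correlation.

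The cost is one sentence and a suppressed p-value, or a wider and approximate interval. Under the assumed curves, a nominal 95% interval from resampling whole subjects within treatment group covered 85% to 93%. The jackknife on Fisher z covered 91% to 95%, with half-widths of 0.06 to 0.25 in Part A and 0.09 to 0.34 in Part B. No new data are needed and no objective changes.

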### Pharmacodynamic Endpoints:

#### *VerifyNow®P2Y12:*

- Minimum %inhibition of PRU within 4 hours after the initiation of study drug. %inhibition of PRU is calculated as  $100 * [(PRU_{bsl} - PRU_{trt})/PRU_{bsl}]$ . PRUbsl refers to the PRU value measured before treatment with ticagrelor and PRUtrt refers to the PRU value measured posttreatment with the study drug.
- PRU area under the curve (AUC) for the first 4 hours.
- Proportion of patients with normalized platelet reactivity units within 4 hours after the initiation of study drug. Normalized platelet reactivity is defined as PRU  $\geq 180$ .
- Proportion of patients with  $\geq 60\%$ ,  $\geq 80\%$ , and 100% of PRU response rate within 4 hours after the initiation of study drug. A PRU response rate is defined as the  $100 * (PRU_{trt}/PRU_{bsl})$ .

- Time to 60%, 80%, 100% of PRU response rate within 4 hours after the initiation of study drug
- Duration of 80% and 100% of PRU response rate by PRU.

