3.2.3. Pharmacodynamic Endpoints

Pharmacodynamic data and parameters will be generated from PRU, LTA and PRI assays:

VerifyNow®P2Y₁₂:

- PRU at each assessment point
- Percent of reversal (%baseline) in ticagrelor antiplatelet activity by PRU at each assessment point
- Maximum PRU
- Maximal percent of baseline PRU
- Time to maximum PRU
- Maximum PRU within 4 hours
- Time to ≥ 180 PRU
- Time to ≥ 200 PRU
- Time to ≥ 220 PRU
- Time to 60%, 80%, and 90% of reversal in PRU

LTA:

- The maximum and final extent of aggregation for up to 4 platelet agonists (20 μ M adenosine diphosphate [ADP], 5 μ M ADP, 1.6 mM arachidonic acid [AA], and 15 μ M thrombin receptor activating peptide [TRAP]), will be recorded at each assessment point.
- Percent of reversal (%baseline) in ticagrelor antiplatelet aggregation
- Maximum platelet aggregation
- Maximum percent of baseline platelet aggregation
- Time to maximum platelet aggregation
- Maximum platelet aggregation within 4 hours
- Time to 60%, 80%, and 90% of reversal in platelet aggregation

VASP by ELISA:

- PRI at each assessment point
- Percent of reversal (%baseline) in PRI at each assessment point
- Maximum PRI
- Maximum percent of baseline PRI
- Time to maximum PRI
- Maximum PRI within 4 hours
- Time to 60%, 80%, and 90% of reversal in PRI
- Time to minimum PRI

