TPRU180	Time to 180 or higher actual PRU, calculated as the first observed time point (no extrapolation) when the actual PRU reaches 180 or above
TPRU200	Time to 200 or higher actual PRU, calculated as the first observed time point (no extrapolation) when the actual PRU reaches 200 or above
TPRU220	Time to 220 or higher actual PRU, calculated as the first observed time point (no extrapolation) when the actual PRU reaches 220 or above
TPRU60%	Time to 60% of baseline PRU, calculated as the first observed time point (no extrapolation) when %baseline PRU reaches 60% or above
TPRU80%	Time to 80% of baseline PRU, calculated as the first observed time point (no extrapolation) when %baseline PRU reaches 80% or above
TPRU90%	Time to 90% of baseline PRU, calculated as the first observed time point (no extrapolation) when %baseline PRU reaches 90% or above

The following PD parameters will be calculated using %baseline/actual MA and FA data, as appropriate, from the LTA assay for both the 5 μ M and 20 μ M ADP conditions.

Day 1 parameters following 5th ticagrelor dose	
APAmx	Maximal actual platelet aggregation
APAmx4h	Maximal actual platelet aggregation within 4 h
PAmax	Maximal percent of baseline platelet aggregation
TPAmx	Time to maximal actual platelet aggregation
TPA60%	Time to 60% of baseline platelet aggregation, calculated as the first observed time point (no extrapolation) when %baseline platelet aggregation reaches 60% or above
TPA80%	Time to 80% of baseline platelet aggregation, calculated as the first observed time point (no extrapolation) when %baseline platelet aggregation reaches 80% or above

TPA90%	Time to 90% of baseline platelet aggregation, calculated as the first observed time point (no extrapolation) when %baseline platelet aggregation reaches 90% or above
--------	---

The following PD parameters will be calculated using %baseline/actual PRI data from the VASP assay.

Day 1 parameters following 5th ticagrelor dose	
APRImax	Maximal actual PRI
APRImax4h	Maximal actual PRU within 4 h
PRImax	Maximal percent of baseline PRI
TPRImax	Time to maximal actual PRI
TPRI60%	Time to 60% of baseline PRI, calculated as the first observed time point (no extrapolation) when %baseline PRI reaches 60% or above
TPRI80%	Time to 80% of baseline PRI, calculated as the first observed time point (no extrapolation) when %baseline PRI reaches 80% or above

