TPRI90%	Time to 90% of baseline PRI, calculated as the first observed time point (no extrapolation) when %baseline PRI reaches 90% or above

Additional PD parameters may be calculated, as necessary. Pharmacodynamic parameters will be listed by subject and summarized for each cohort using descriptive statistics (number of subjects, mean, SD, median, minimum, and maximum). Number and percent of subjects achieving 60%, 80%, and 90% of reversal in PRU, LTA, and PRI within 30 minutes or 4 h will be summarized.

12. Interim Analysis

There is no interim analysis planned for this study.

13. Changes in the Planned Analysis

There is no change in the SAP compared to the protocol

14. References

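### SAP 11.2 drops the protocol's 4-hour limit on time to reversal, replaces 100% with 90%, and has no rule for subjects who never reach the threshold, while SAP Section 13 declares no change

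*SAP*

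**What the plan says.** The synopsis of each protocol part lists as a PRU endpoint "Time to 60%, 80%, 100% of PRU response rate within 4 hours after the initiation of study drug", and Section 2.2.2 repeats it. The LTA and VASP endpoints carry the same three thresholds and the same limit.

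SAP 3.2.3 lists "Time to 60%, 80%, and 90% of reversal in PRU" with no limit. SAP 11.2 then defines TPRU60% as "Time to 60% of baseline PRU, calculated as the first observed time point (no extrapolation) when %baseline PRU reaches 60% or above". The 80% and 90% versions, the LTA (TPA) and VASP (TPRI) versions, and TPRU180, TPRU200 and TPRU220 all use the same first-observed-crossing rule. The same tables contain a separate row for "Maximal actual PRU within 4 h" beside the unrestricted maximum.

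The tables are headed "Day 1 parameters following 5th ticagrelor dose"; the SAP does not say what span Day 1 covers. PD sampling runs "up to 48 hours after the initiation of study drug infusion", at "5 minutes, 0.25, 0.5, 1, 2, 4, 8, 12, 20, 24, 36 and 48 hours after initiation of PB2452 or placebo infusion". The parameters are to be "summarized for each cohort using descriptive statistics (number of subjects, mean, SD, median, minimum, and maximum". Missing PD measurements stay missing, and no rule covers a threshold that is not reached.

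SAP 11.2 also plans a count and percentage of subjects reaching 60%, 80% and 90% at 30 minutes or 4 hours, and a by-subject listing. Section 13 states that nothing differs from the protocol.

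**The concern.** Time to reversal is a natural headline for a reversal agent, and PRU reversal is a primary objective in both parts. Two gaps make its summary hard to interpret.

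- **No window.** Ticagrelor's effect wears off without any antidote. If late samples are eligible, a subject whom the study drug did not reverse can still receive a time to reversal once wash-out carries the reading over the threshold. Placebo subjects can receive one in the same way.
- **No not-reached rule.** A subject who never crosses has no first crossing. With ordinary descriptive statistics, a programmer would most likely leave that subject out, so the mean, SD and median would describe only those who crossed.

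The first gap lengthens the mean; the second shortens it. The SAP does not settle which applies to a given subject. With 6 to 9 active subjects per cohort, one or two subjects can dominate the result. Because Section 13 reports no change, a reader of the study report would reasonably take these figures to be the protocol's 4-hour endpoint.

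**Working it through.** The documents give no figure for these parameters, so there is none to reproduce. The check is a count of sampling times, a reading of the tables, and an illustration.

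**1. Sampling times against the window.** The 12 post-dose times in SAP 11.1 split as follows:
- at or before 4 h: 5 min, 0.25, 0.5, 1, 2, 4 h (6 times)
- 8, 12, 20, 24 h (4 times)
- 36, 48 h (2 times)

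With no window, 4 + 2 = 6 of 12 lie outside the protocol limit. If Day 1 means 0 to 24 h, 4 remain eligible although outside it.

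**2. Is 4 hours implied?** The tables give the maximum twice, once unrestricted and once limited to 4 h. If 4 h were the default for every row, the second row would be redundant. The time-to-threshold rows carry no such label.

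**3. Illustration.** SAP 3.1 gives 8 to 12 subjects per cohort at 3:1, so 8 × 3/4 = 6 to 12 × 3/4 = 9 active. Assumptions not in the documents: reversed subjects cross at 5 min (5/60 = 0.083 h), and k subjects are not reversed by 4 h but cross by wash-out at t = 12, 24 or 36 h.

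- No window: mean = [(n − k) × 0.083 + k × t] / n
- 4 h window, crossers only: mean = 0.083 h on n − k subjects
- Share reached by 4 h = (n − k) / n

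| n, k | No-window mean, t = 12 / 24 / 36 h | Crossers-only mean | Reached by 4 h | Median, censored at 4 h |
|---|---|---|---|---|
| 9, 2 | 2.73 / 5.40 / 8.06 h | 0.083 h (7 subjects) | 7/9 = 77.8% | 0.083 h |
| 9, 5 | 6.70 / 13.37 / 20.04 h | 0.083 h (4 subjects) | 4/9 = 44.4% | not reached |
| 6, 2 | 4.06 / 8.06 / 12.06 h | 0.083 h (4 subjects) | 4/6 = 66.7% | 0.083 h |

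First row written out for t = 12: (7 × 0.083 + 2 × 12) / 9 = 24.58 / 9 = 2.73 h.

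Without a window, late subjects stay in and lengthen the mean. With a window but no censoring rule they drop out, and the mean is 0.083 h whether 2 or 5 of 9 fail.

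**4. What the responder table covers.** It covers 60%, 80% and 90% for all three assays. It does not cover TPRU180, TPRU200 or TPRU220. The protocol's proportion of subjects with PRU of at least 180 by 4 h does not appear in SAP 3.2.3 or Section 11.

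**The case against.** A reader might infer that the SAP averages times only among reachers, over 48 hours, so that non-responders vanish. The documents do not support that.

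- **Neither rule is written.** Leaving out non-crossers is the likely result of having no rule, but it is not stated. The 48-hour span is inferred from the sampling schedule. Day 1 may mean 0 to 24 h; Protocol Part A separates Day 1 from Day 2 PD parameters for cohorts given a sixth ticagrelor dose.
- **Non-responders remain visible** for 60/80/90%, through the responder table, the number of subjects in each summary, and the listing.
- **The most striking example is fragile.** Suppose regimen A reverses 9 of 9 (six at 5 min, three at 4 h), with mean (6 × 0.083 + 3 × 4) / 9 = 1.39 h, and regimen B reverses only 6 of 9 at 5 min, with mean 0.083 h among crossers. B looks about 17 times faster (1.39 / 0.083). This requires B's three failures never to cross. If they cross at 12 h, B's mean is (0.5 + 36) / 9 = 4.06 h and B correctly looks slower. The median is 5 min in both regimens, censored or not. Only 9/9 against 6/9 separates them.
- **The consequences are modest.** No hypothesis test on these times is specified, and Part B calls its efficacy results descriptive. SAP 3.1 and 3.3 record the cohorts and dose levels as already enrolled, so this final analysis did not drive cohort selection. Phase 1 reported reversal to about 100% of baseline at the first assessment for 3 to 18 g, so many failures may not occur.
- **There is no protocol window to restore** for TPRU180, TPRU200 or TPRU220, because the protocol has no such time endpoints.

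All of this stands, and it limits the size of the point. It does not explain the missing window, the threshold change, the absent rule, or the statement in Section 13.

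**Conclusion.** The concern holds as an undeclared protocol-SAP discrepancy combined with a missing analysis rule. The 4-hour limit is gone from time to 60% and 80%, 100% has become 90%, and subjects who do not cross have no defined handling. Depending on how the gap is filled, the time summary either mixes wash-out with drug effect or conditions on having crossed.

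The sponsor should correct it, but it does not undermine the study. The effect is confined to the time summaries; the 4-hour responder proportions for 60/80/90% are retained. For TPRU180, TPRU200 and TPRU220 no matching responder table is planned, so only the summary count and listing would show who failed to reach them.

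The count of 6 (or 4) sampling times outside the window comes directly from the SAP. The hour values are illustrative and rest on assumed crossing times and failure numbers. They also take the pre-ticagrelor value as baseline, as the protocol does for PRU.

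**What to change.** In SAP 3.2.3 and 11.2:

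1. Apply the 4-hour window to the time-to-60/80/90% parameters for PRU, LTA and PRI. Use the same window for TPRU180, TPRU200 and TPRU220 for consistency.
2. Censor subjects who have not crossed at 4 h, or at their last PD sample if earlier.
3. For each treatment group, report number reached over N beside a Kaplan-Meier median, in place of the mean and SD among reachers. Reached over N is the more informative figure, since the median can coincide when success rates differ.
4. Present any longer-window version separately and label it as such.
5. In Section 13, declare the window change (if any part of it is kept) and the change from 100% to 90%.

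The cost is SAP wording and programming, with no new data. In some groups the median may have to be reported as not reached.

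### SAP Section 13 declares no change from the protocol, yet none of the protocol's 16 PD endpoint lines is carried over unchanged: 6 are absent, 1 is replaced and 9 are altered

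*SAP*

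**What the plan says.** The protocol lists its PD endpoints in the synopsis and in Section 2.2.2 of each part, and the Part A and Part B lists are the same. Every assay has five lines:

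- minimum %inhibition within 4 h;
- AUC over the first 4 h;
- proportions reaching 60%, 80% and 100% of baseline within 4 h;
- time to 60%, 80% and 100% within 4 h;
- duration of 80% and 100% response.

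PRU has a sixth: the proportion reaching at least 180 within 4 h. The PRU baseline is the value before ticagrelor.

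The SAP sets its parameters in Sections 3.2.3 and 11.2. They include "Maximum PRU within 4 hours" and "Percent of reversal (%baseline) in ticagrelor antiplatelet activity by PRU at each assessment point", maximal percent of baseline with no time limit, time to 180, 200 and 220 PRU, and time to 60%, 80% and 90%. An example of the last is "Time to 90% of baseline PRU, calculated as the first observed time point (no extrapolation) when %baseline PRU reaches 90% or above". The proportions are given as "Number and percent of subjects achieving 60%, 80%, and 90% of reversal in PRU, LTA, and PRI within 30 minutes or 4 h". Raw results are also reported: "Pharmacodynamic data will be listed by subject and ADA status and summarized for each treatment group for each time point using descriptive statistics".

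Section 13 then states: "There is no change in the SAP compared to the protocol".

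**The concern.** Reversal of ticagrelor measured by PRU, against placebo, is a primary objective in both parts. The Section 13 sentence tells a reader that the protocol's PD summaries will all appear, when several will not.

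Duration matters most. Protocol Section 1.1.2 links duration of reversal to total dose and infusion duration, and Section 1.1.3 cites 20-24 h from Phase 1. In a dose- and regimen-finding study, the SAP derives no duration for any of the three cohorts in its Section 3.3 (18 g, 18 g and 36 g). Nor will AUC over 4 h or the attainment of full baseline be summarised.

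A related gap concerns baseline. SAP Section 4 has one definition, the last non-missing value before study drug, and no PD exception. Read literally, that is the Hour 0 sample taken on ticagrelor, which conflicts with the protocol's PRU baseline.

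**Working it through.** The SAP gives no count or figure to reproduce, and no power or alpha is involved. The check sets the lists side by side.

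**Rule.** Absent: the SAP has no parameter for the line. Replaced: a different kind of summary. Altered: the same summary with a changed threshold or window.

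| Protocol line | SAP 3.2.3 / 11.2 | Class | PRU | LTA | VASP |
|---|---|---|---|---|---|
| Minimum %inhibition within 4 h | Maximal percent of baseline, no window; also maximal actual value within 4 h | Altered | 1 | 1 | 1 |
| AUC over first 4 h | None | Absent | 1 | 1 | 1 |
| Proportion with PRU at least 180 within 4 h | Time to 180 or higher | Replaced | 1 | - | - |
| Proportion at 60/80/100% within 4 h | 60/80/90%, 30 minutes or 4 h | Altered | 1 | 1 | 1 |
| Time to 60/80/100% within 4 h | 60/80/90%, no window | Altered | 1 | 1 | 1 |
| Duration of 80% and 100% | None | Absent | 1 | 1 | 1 |

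Lines: 6 + 5 + 5 = 16. Absent 3 + 3 = 6; replaced 1; altered 3 + 3 + 3 = 9. 6 + 1 + 9 = 16, so 0 are unchanged.

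**Why the first row is altered, not replaced.** The protocol's PRU formulas are %inhibition = 100 × (bsl − trt)/bsl and response = 100 × trt/bsl. On one baseline, %inhibition = 100 − response. Minimum %inhibition is therefore 100 minus maximal percent of baseline over the same window. (The protocol writes out the %inhibition formula only for PRU; the same form is assumed for LTA and PRI.) The window still matters. Take invented PRU values: baseline 250, highest value 235 within 4 h, and 245 later. Minimum %inhibition within 4 h is 100 − 100 × 235/250 = 6%. Without the window it is 100 − 100 × 245/250 = 2%.

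**Single components.** Splitting each line into its thresholds gives 3 (minimum %inhibition) + 3 (AUC) + 1 (PRU 180) + 9 (proportions) + 9 (time-to) + 6 (duration) = 31. Of these:

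- 9 are absent (3 AUC, 6 duration);
- 1 is replaced;
- 6 move from 100% to 90%;
- 3 (minimum %inhibition) change to the complement and lose the window;
- 6 (time to 60% and 80%) lose only the 4 h limit;
- 6 (proportions at 60% and 80% within 4 h) are kept.

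9 + 1 + 6 + 3 + 6 + 6 = 31.

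**Can the missing summaries be computed?** SAP Section 11.1 schedules Hour 0, 5 minutes, 0.25, 0.5, 1, 2 and 4 h, which is 7 points for AUC over 4 h. Later samples are at 8, 12, 20, 24, 36 and 48 h, with gaps of 4, 4, 8, 4, 12 and 12 h. So an observed duration is resolved to about 4 h if reversal ends between 20 and 24 h, and only to 12 h if it ends later.

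**Baseline, literal reading.** A subject unchanged from Hour 0 has percent of baseline = 100 × PRU(0)/PRU(0) = 100%, and so would pass the 60%, 80% and 90% thresholds without any reversal.

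**Smaller slips.** SAP Section 3.2.3 lists "Maximum PRI within 4 hours", but Section 11.2 describes the matching VASP parameter, APRImax4h, as "Maximal actual PRU within 4 h". SAP Section 11 analyses a PD population that Section 4.5 does not define and Section 5.1 does not list, although both protocol parts define it in Section 3.6.2.

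**The case against.** The strongest reply is that little is really lost. Percent of baseline is reported at every assessment point for all three assays and carries the same information as %inhibition. The proportion with PRU at least 180 within 4 h can be read subject by subject from the maximal actual PRU within 4 h, and times up to 4 h can be read from uncapped times. A count of zero unchanged lines also depends on bundling three thresholds into one line. Both documents allow additional PD parameters. Results are descriptive in any case.

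Most of this stands. Part B Section 3.6.3.2 calls efficacy results descriptive, and Part A plans only descriptive statistics. The added 90%, 200/220 PRU and 30-minute parameters are permitted. But permission to add is not permission to drop without saying so. AUC over 4 h, duration and the 100% threshold cannot be obtained from any planned parameter. They would have to be worked out from listings.

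On baseline, the documents point away from the literal reading. The SAP speaks of percent of reversal, the protocol visits labelled as baseline that carry PD sampling are Days -3 and -2, and SAP Section 11.1 times the Day -2 sample before the first ticagrelor dose. What remains is a missing sentence, not a demonstrated error.

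**Conclusion.** The Section 13 statement is wrong as written and should be corrected. All 16 PD lines differ: 6 absent, 1 replaced, 9 altered. The substantive losses are derived AUC over 4 h, duration of response and the 100% threshold in all three assays, and the tabulated 180 PRU proportion.

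Three stronger readings are tempting but unsupported:

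- That the SAP leaves Part B's optional %inhibition comparison without a variable. Percent of baseline is its exact complement on the same baseline, so a treatment difference only changes sign.
- That the primary PD assessment is invalidated. No PD endpoint is ranked as primary, results are descriptive, no error rate is affected, and the raw course stays visible in listings, time-point summaries and box plots.
- That thresholds were changed after seeing data. The SAP describes the cohorts as already enrolled, and Section 4.2 gives designated sponsor staff unblinded data after each cohort's Day 3. Nothing says those data informed the endpoints. An accurate change list is what would settle the question.

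The count does not depend on whether a line is labelled replaced or altered. It does assume that the protocol text here is the version the SAP was written to. SAP Section 1 cites Final 2.0 (Part A) and Final 1.0 (Part B), and with title pages removed this cannot be confirmed.

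**What to change.** In SAP Sections 3.2.3 and 11.2:

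- For PRU, LTA and PRI, reinstate AUC over the first 4 h, duration of at least 80% and at least 100% response, and the 100% threshold in the proportion and time-to lines.
- Report maximal percent of baseline (equivalently minimum %inhibition) within 4 h.
- For PRU, reinstate the proportion reaching at least 180 within 4 h.
- Prespecify one duration rule, since the protocol gives none. Say how a dip with later recovery is counted, and how subjects still above threshold at the last sample are counted. Note the 4 to 12 h sampling gaps after 4 h.
- State that PD percent of baseline and %inhibition use the pre-ticagrelor value, not the Section 4 baseline. Using Day -2, or Day -3 if that is missing, is my suggestion; the protocol says only that the value precedes ticagrelor.
- Keep the 90%, 200/220 PRU and 30-minute parameters, labelled as additional.

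Replace the Section 13 sentence with a list of every remaining difference from the protocol, including any line not reinstated, each with its reason. As minor corrections, change the APRImax4h description to PRI and add the protocol's PD population to Sections 4.5 and 5.1.

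The cost is an SAP amendment plus a few derivations and tables. Every sample needed is already in the schedule.
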